1. hyperglycemia increases metabolism both by increasing the amount of glucose to be reabsorbed, but via hyperfiltration also the amount of sodium to be reabsorbed. The sodium-glucose cotransport is a very energy(oxygen)-consuming process.
2. sustained hyperglycemia increases oxygen demand by reducing the metabolic efficiency, due to mitochondrial dysfunction and reduced efficiency of electrolyte transport
3. increased angiotensin-II receptor activity and oxidative stress can further reduce the metabolic efficiency of electrolyte transport
4. Increased oxygen demands cannot be met by increased blood flow, because this will further increase metabolism by increasing the filtered load of solutes

Blood-oxygen-dependant level magnetic resonance imaging

Renal blood oxygenation can be measured with magnetic resonance imaging (MRI) by using the paramagnetic property of deoxyhemoglobin as a surrogate measure. The blood oxygen level magnetic (BOLD) imaging signal is expressed by the transverse relaxation time (T_2^*). T_2^* measurements do not differentiate between oxygen delivery and oxygen consumption and for this reason it has been suggested that measurement of renal blood flow is mandatory to interpret renal T_2^* values. Renal artery flow can be measured using phase contrast (PC) MRI. Renal tissue perfusion can be measured noninvasively with MRI using arterial spin labelling (ASL) (15). Renal oxygen consumption has not previously been measured but hypothetically

it can be estimated with Q-flow combined with measurement of BOLD in the renal artery and vein.

Mitochondrial function

Mitochondria play an important role in aerobic metabolism. Thus, it is assumed that generalized or local mitochondrial dysfunction can contribute to an increased oxygen demand in the kidneys. Mitochondrial dysfunction can be quantified through extracellular flux analysis on peripheral blood mononuclear cells (PBMCs) which are easily accessible from a blood sample. This method gives information about a variety of measures of mitochondrial function including basal respiration, ATP production, proton leak and maximal respiration. Technical details and interpretive value of this method have been well described (16).

Autonomic function

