We hypothesize that SGLT2 inhibition acutely reduces the kidneys demand for oxygen by reducing renal metabolism due to blocked sodium-glucose transportation, and hyperfiltration. We hypothesize that the following changes can be demonstrated after institution of SGLT2 inhibition:

- 1) Lowering of renal artery flow (PC-MRI)
- 2) Lowering of renal cortical perfusion and the ratio of cortical/medullary perfusion (ASL-MRI)
- 3) Better medullary oxygenation: Lowering of the renal medulla T_2^* (BOLD-MRI)
- 4) Decrease of renal oxygen consumption (Q-flow combined with measurement of BOLD in renal artery and vein)

We further hypothesize that autonomic function will improve, and that peripheral blood oxygenation and mitochondrial function will both increase after institution of SGLT2 inhibition.

Study population

Fifteen healthy controls recruited through an advertisement in the local newspapers and 15 persons with type 1 diabetes recruited from Steno Diabetes Center Copenhagen according to the study in-and exclusion criteria.

Inclusion criteria healthy controls:

- Written informed consent must be provided before participation
- Male or female patients > 18 years of age
- Capable of lying in a MR-scanner for two hours

Inclusion criteria persons with type 1 diabetes:

- Written informed consent must be provided before participation
- Male or female patients >18 years of age with a diagnosis of type 1 diabetes (WHO criteria)
- Urinary albumin creatinine ratio (UACR) ≥ 30 mg/g in 2 out of 3 consecutive samples (albuminuria) prior to randomization assessed from electronic laboratory database.
- Capable of lying in a MR-scanner for two hours

Exclusion criteria for all:

- Non-diabetic kidney disease as indicated by medical history and/or laboratory findings
- Renal failure (eGFR<15 ml/min/1.73m²), dialysis or kidney transplantation
- Treatment with beta-blocking medication
- Uncontrolled arrhythmia, 2. or 3. degree AV-block or sick sinus syndrome - assessed from a standard 12-lead electrocardiogram
- Pregnancy or breastfeeding (urine HCG is performed on all fertile women)
- Systolic blood pressure < 90 or > 200 mmHg
- Patients who, in the judgement of the investigator, is incapable of participating
- Exclusion criteria for MRI
 - Claustrophobia
 - Known heart disease

- Known lung disease
- Have had surgery the past six weeks
- Have foreign bodies of metal in the body (e.g. pacemaker, metal plates, metal screws)

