Information about civil registration number, phone number, address, diagnosis of T1D and historic levels of urine albumin on outpatients at Steno Diabetes Center Copenhagen is provided by the treatment-responsible doctor and passed on to the study investigator. This information is used for identifying possible participants and recruitment. First contact will be a letter containing the written participant information and the brochure: "Your rights as a participant in biomedical research". In the letter, possible participants will be invited to the information meeting at Steno Diabetes Center Copenhagen. The letter contains telephone number and email for the project-responsible doctor. Non-responders will be followed up by a telephone contact approximately two weeks later. All who wish to participate in the study are invited for an information visit.

Healthy controls will be recruited by advertisement in the local newspapers. In the advertisement, there will be phone number and email of the investigators for contact.

Endpoints

Primary end-point

- Renal oxygenation (T_2^*)

Exploratory end-points

[figure not shown]
- Renal cortical and medullary perfusion
- Renal artery flow
- Renal oxygen consumption
- Peripheral capillary oxygen saturation (SpO_2)
- Arterial blood gasses
 - Arterial blood oxygen partial pressure (PaO_2)

- Arterial blood oxygen saturation (SaO₂)
- PBMC mitochondrial function
- Circulating inflammatory markers
- Baroreflex sensitivity

Study design

Randomized, double blinded, placebo-controlled, cross-over intervention study in patients with type 1 diabetes. Baseline results will be compared to healthy controls.

Figure 1

Flowchart of study design. Healthy controls (CON) will only come for baseline measurements on V1 and V2, except blood gas analysis, which will only be done in randomized patients.

Patients with type 1 diabetes (T1D) will be randomized to SGLT2i or placebo for Visits 1+2 and crossed over for Visits 3+4.

Comparative treatment regimes

Patients in the active arm will be treated with dapagliflozin 50 mg once on site for V2 and once at home on the evening before V3.

Randomization and blinding

Patients will be randomly assigned in a 1:1 ratio to one of the following groups:

- Dapagliflozin for V2 and V3 and placebo for V4 and V5
- Placebo for V2 and V3 and dapagliflozin for V4 and V5

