All events meeting the definition of an AE must be collected and reported. This includes events from the first study-related activity after the subject has signed the informed consent until the end of the study. When reporting Adverse Events the following parameters must be recorded: study name, patient identification (subject number, initials, sex, age), event (preferably a diagnosis), IMP, reporter identification (name or initials), causality, outcome. Timelines for reporting of AE's is described in study timetable.

Assessment of adverse event

The following three definitions are used when assessing the severity of an AE: Mild (no or transient symptoms, no interference with the subject's daily activities), Moderate (marked symptoms, moderate interference with the subject's daily activities) and Severe (considerable interference with the subject's daily activities; unacceptable).

The following terms are used when assessing the causality between an AE and the IMP: Probable (good reason and sufficient documentation to assume a causal relationship), Possible (a causal relationship is conceivable and cannot be dismissed) and Unlikely (the event is most likely to ethology other than the IMP (Forxiga®).

Reporting at the end of the study

A final report on the AEs and SAEs is sent to the Danish Medicines Agency, the Regional Scientific Ethics Committee and to AstraZeneca within 12 months after the last patient has completed the project.

Statistical considerations

Sample size

The primary goal is to test the hypothesis that SGLT2 inhibition will improve renal oxygenation with a lowering of medullary T_2^* , as a marker of increased oxygenation. A power calculation was performed, based on data available from the study by Haddock. et al. (15). The mean \pm SD resting medullary T_2^* was 23 ± 4 . Assuming that SGLT2 inhibition will improve oxygenation 20%, the sample size required to demonstrate a significant effect with a power of 80% and a type 1 error of 5%, is 13 subjects per group. To account for technical difficulties, we included 15 in each group. Power calculation was performed using the power statement implemented in the SAS enterprise software 7.1 (SAS Institute, Cary, NC, USA).

Analysis

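### The primary hypothesis has the T2* direction reversed: a lower medullary T2* is called better oxygenation, so a fall in kidney oxygenation would be read as a drug benefit

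*Combined protocol and SAP*

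**What the plan says.** Two places give a direction for T2*, and they agree with each other.

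- **Hypothesis, item 3:** "Better medullary oxygenation: Lowering of the renal medulla T_2^* (BOLD-MRI").
- **Statistical considerations, Sample size:** the primary goal is to show that SGLT2 inhibition will "improve renal oxygenation with a lowering of medullary T_2^* , as a marker of increased oxygenation".

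The Background section on BOLD imaging gives the measurement principle. Oxygenation is measured by "using the paramagnetic property of deoxyhemoglobin as a surrogate measure", and the "imaging signal is expressed by the transverse relaxation time (T_2"*), which is a time and not a rate.

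The Sample size section then sets the numbers: "SD resting medullary T_2^* was 23", with SD 4 and no unit; "Assuming that SGLT2 inhibition will improve oxygenation 20" per cent; and, for "a power of 80% and a type 1 error of 5%, is 13 subjects per group". The Endpoints section names T2* as the primary endpoint without a direction. The Analysis section specifies two-tailed testing at 0.05 and also gives no direction.

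**The concern.** A paramagnetic substance speeds up transverse dephasing and so shortens T2*. If oxygenation improves, there is less deoxyhaemoglobin and T2* lengthens. The protocol predicts a shortening and calls it improvement, against the principle it cites. The same reversal in both places makes an isolated slip unlikely.

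This is the direction of success for the only endpoint with a power calculation. A significant fall in T2* after dapagliflozin, meaning more deoxyhaemoglobin, would confirm the hypothesis as written. A significant rise would count against it.

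A fall is not a remote possibility. The same hypothesis list predicts lower renal artery flow and lower cortical perfusion, and the Background says that T2* does not separate oxygen delivery from consumption.

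The reversed scale could also carry over to the baseline comparison with healthy controls. A lower T2* in patients would read as better oxygenation, contrary to the hypoxia in diabetic kidney disease that the Background describes.

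**Working it through.** **Inputs.** From the Sample size section: mean medullary T2* 23, SD 4, improvement 20%, power 80%, type 1 error 5%, 13 per group raised to 15. From the Analysis section: two-tailed test. Assumption: T2* is in milliseconds, since no unit is given. This affects only the absolute R2* values below, not the percentage changes.

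**1. Reproduce the plan's sample size.** Difference = 0.20 × 23 = 4.6; standardised difference = 4.6 / 4 = 1.15.

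- Normal approximation: n = 2 × (1.960 + 0.842)² / 1.15² = 11.9, so 12 per group.
- Two-sample t-test (noncentral t): n = 12.90, so 13 per group, with power 80.3% at 13 and 86.0% at 15.

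The stated 13 is reproduced by an unpaired two-sample t-test with a 4.6 change in T2*.

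**2. Direction from the protocol's own principle.**

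- Background: the contrast comes from paramagnetic deoxyhaemoglobin, and the readout is T2*, a relaxation time.
- Inference from basic MR physics, not written out in the protocol: more deoxyhaemoglobin gives faster dephasing and a shorter T2*.
- Therefore better oxygenation means higher T2* and lower R2*. The Hypothesis and Sample size sections say lower T2*.

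**3. What the planned effect means in each direction.** R2* = 1000 / T2* (per second, with T2* in ms).

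| | T2* | R2* | Change in R2* | Deoxyhaemoglobin |
|---|---|---|---|---|
| Resting | 23 | 1000/23 = 43.5 | – | – |
| As written (23 − 4.6) | 18.4 | 1000/18.4 = 54.3 | 1/0.8 − 1 = +25% | more |
| Sign corrected (23 + 4.6) | 27.6 | 1000/27.6 = 36.2 | 1/1.2 − 1 = −16.7% | less |

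**4. Effect of the sign on n and power.** A two-sided calculation uses only the size of the difference. For −4.6 and for +4.6 it gives 13 per group and 80.3% power.

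**5. Which conclusion the written hypothesis would reach.** Suppose the true change is +4.6, with 13 per group compared by an unpaired t-test. The noncentrality is 4.6 / (4 × √(2/13)) = 2.93 on 24 degrees of freedom. The test is then significant upward with probability 80.3%, and significant in the written, downward direction with probability about 0.0000009. A true benefit of the planned size would almost never support the hypothesis as worded.

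**The case against.** The strongest reply is that nothing in the analysis depends on the sign. The endpoint is named without direction, response to dapagliflozin is simply compared with response to placebo, and the test is two-tailed. Estimate, interval, p-value, n and power all stand, and a careful author could still interpret the result correctly. Flow, perfusion and oxygen consumption are measured in the same MRI sessions, which gives further protection against a naive reading. This part stands: the misreading is what the written plan implies, not a certainty. But a correct reading would mean reversing the stated primary hypothesis after seeing the data, which is hard to tell from post hoc reinterpretation.

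A second reply is that the symbol may be the slip, and R2* was meant. The document calls the quantity T2* in the Background, Hypothesis, Endpoints, Methods and Sample size sections and never mentions R2*. If R2* was intended, the endpoint label must change, and the 23 ± 4 must be checked. Either way the text is wrong. Confirming the quantity and unit before amending is reasonable.

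Third, the plan assumes that oxygenation improves by 20%, not expressly that T2* changes by 20%. A 20% fall in R2* would take T2* to 23 / 0.8 = 28.75, a difference of 5.75, and with SD 4 would need 9 per group. Analysed on the R2* scale with the same coefficient of variation, it needs 13. Neither needs more than 13, and the match at 12.90 supports the 4.6 reading.

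Finally, the Background's caveat that T2* does not separate delivery from consumption limits how a change in T2* is explained. It does not reverse the link between deoxyhaemoglobin and T2*.

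**Conclusion.** The concern holds, and the correction is essential. Both sentences that give a direction for the primary endpoint have it backwards relative to the measurement principle in the same protocol, and no other section corrects them. The planned improvement as written (23 to 18.4) is a 25% rise in R2*, which is a loss of oxygenation. The intended benefit on the T2* scale is 23 to 27.6, a 16.7% fall in R2*.

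The error lies in the hypothesis and its interpretation, not in the arithmetic: 13 per group, 80.3% power and the two-sided p-value are unaffected. The conclusion rests on one inference that the protocol does not spell out, that paramagnetic deoxyhaemoglobin shortens T2*, and on the endpoint being T2*, as it is labelled throughout.

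**What to change.** After confirming that the quantity is T2* and stating its unit, amend two places:

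- **Hypothesis, item 3:** replace the lowering of medullary T2* with an increase in medullary T2*, equivalently a decrease in R2* = 1/T2*.
- **Sample size:** make the same replacement, state that a positive dapagliflozin-minus-placebo difference in T2* is improved oxygenation, and give the planned effect as +4.6 (23 to 27.6).

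The same reading of the scale should apply to the baseline comparison with healthy controls. Date the amendment before unblinding; if that point has passed, disclose the correction openly in the report. The cost is two sentences, with no operational change, no new data and no change to n on the T2* scale.

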- Exclusion criteria for arterial blood gas sampling (only patients with type 1 diabetes)
 - Absent pulse
 - Raynauds syndrome
 - Buergers Disease (thromboangiitis obliterans)
 - Inadequate or interrupted circulation
 - Anticoagulation treatment
 - Coagulopathies (hypo or hyper coagulable states)
 - Arterial atherosclerosis
 - Insufficient collateral perfusion
 - Partial or full thickness burns over the cannulation site
 - Synthetic arterial or vascular grafts or infection at the proposed site of cannulation

Patients with type 1 diabetes will have the possibility to participate in the study without getting arterial blood gas sampling.

- Healthy control exclusion criteria
 - The subject has a clinically significant abnormal laboratory value and/or clinically significant medical or psychiatric illness.
 - The subject has evidence of clinically significant gastrointestinal, cardiovascular, hepatic, renal, hematological, neoplastic, endocrine, neurological, immunodeficiency, pulmonary, or other disorder or disease.

Patient withdrawal

In case of pregnancy (or desire for pregnancy), female subjects are withdrawn.

Lack of compliance to any of the important study procedures in the discretion of the investigator.

Onset of any disorder considered to compromise the safety by participating in the study.

Unacceptable adverse effects in the discretion of the investigator.

Withdrawal on participants request will be accepted at any time without further justification or consequence to regular treatment at the Steno Diabetes Center Copenhagen.

Withdrawn patients will be replaced by patients recruited in the same manner as described in this protocol.

Recruitment

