Mitochondrial function		x		x		x
Inflammatory markers		x		x		x
Baroreflex sensitivity		x		x		x
Kidney MRI			x		x	
Pulse oximetry			x		x	
Blood gas analysis			x		x	
Safety						
Adverse events			x	x	x	x
Study medication						
Drug accountability				x		x

Study timetable for randomized patients. SDCC = Steno Diabetes Center Copenhagen, RHG = Rigshospitalet Glostrup.

Assessment of efficacy

In order to assess the acute physiological response of inhibiting SGLT2 in the proximal tubule, kidney MRI parameters, pulse oximetry and blood gas analysis are obtained before intervention (baseline), three hours after intervention and six hours after intervention. In order to assess the subacute, systemic physiological response, PBMC mitochondrial function, inflammatory markers and baroreflex sensitivity are obtained before intervention (baseline) and 12 hours after intervention. Baseline levels will be compared to those of healthy controls.

Response to dapagliflozin in outcomes in randomized patients will be compared to response to placebo.

Assessment of safety

Definition of SAE, SAR and SUSAR

Serious Adverse Event (SAE):

A Serious Adverse event is an experience that treatment results in any of the following:

- Results in death
- Is life threatening (note: the term life-threatening refers to an event in which the patient was at risk of death at the time of the event; it does not refer to an event which hypothetically might have caused death if it was more severe)
- Requires inpatient hospitalization or results in prolongation of existing hospitalization
- Results in persistent or significant disability/incapacity
- Is a congenital anomaly/birth defect, or
- Is an important medical event that may not result in death, be life-threatening, or require hospitalisation may be considered a serious adverse event when, based upon appropriate medical judgement, they may jeopardise the patient or subject and may require medical or surgical intervention to prevent one of the outcomes listed in this definition.
- Suspicion of transmission of infectious agents must always be considered an SAE.

Serious Adverse Reaction (SAR):

A SAE for which a causal relationship to the study medication is at least possible i.e. a causal relationship is conceivable and cannot be dismissed.

Suspected Unexpected Serious Adverse Reaction (SUSAR):

A SAE which is unexpected and regarded as possibly or probably related to the study medication by the Investigator.

Reporting of SAE SAR and SUSAR

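### The 13 per group for 80% power is reproduced by an unpaired two-group test, but the drug effect is a cross-over within 15 patients, and the within-patient SD it needs is not stated

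*Combined protocol and SAP*

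**What the plan says.** Statistical considerations, Sample size, sets the goal of showing that SGLT2 inhibition changes medullary T2*. It takes a resting mean of 23 and SD of 4 from a cited imaging study, assumes a 20% improvement, and reports that the number needed "with a power of 80% and a type 1 error of 5%, is 13 subjects per group". It then adds: "To account for technical difficulties, we included 15 in each group". It names no test and no within-patient SD or correlation.

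Study population identifies the two groups: "Fifteen healthy controls recruited through an advertisement in the local newspapers and 15 persons with type 1 diabetes". Study design describes a "Randomized, double blinded, placebo-controlled, cross-over intervention study in patients with type 1 diabetes", and the legend to Figure 1 adds: "Healthy controls (CON) will only come for baseline measurements on V1 and V2". Assessment of efficacy separates two comparisons. For the drug: "Response to dapagliflozin in outcomes in randomized patients will be compared to response to placebo". For the controls: "Baseline levels will be compared to those of healthy controls".

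The Analysis section tests the intervention by linear regression adjusted for the baseline value, uses an unpaired t-test for group differences, and sets a two-tailed 5% level. It names no patient or period term. Patient withdrawal states: "Withdrawn patients will be replaced by patients recruited in the same manner as described in this protocol".

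**The concern.** A per-group number for the drug effect implies that one set of people is treated and a different set is not. Here each randomised patient receives both treatments, and the second group of 15 never receives study drug. The precision of the drug contrast depends on how much T2* varies within a patient between periods, whereas the section gives a resting SD across subjects.

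At stake is whether the 80% can be relied on. If the primary end-point shows no effect, a reader will want to know whether the trial could have detected 4.6, and the document does not allow that to be worked out. The allowance from 13 to 15 in each group has the same fault, since two more controls add nothing to the drug test.

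**Working it through.** **Inputs.** Sample size: mean 23, SD 4, effect 20%, power 80%, type 1 error 5%. Analysis: two-tailed. The effect is δ = 0.20 × 23 = 4.6.

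**Step 1: reproduce the plan's figure.** For an unpaired t-test with n per group, the noncentrality is λ = δ / (4√(2/n)) on 2n − 2 df.

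| n per group | λ | Power |
|---|---|---|
| 12 | 2.82 | 76.8% |
| 13 | 2.93 | 80.3% |
| 15 | 3.15 | 86.0% |

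Thirteen is the smallest n that reaches 80%, so the printed inputs give the printed answer.

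**Step 2: try other readings.**
- A paired test with 4 as the SD of the difference needs 9 patients, not 13.
- A paired test returns 13 if the SD of the difference lies between 5.18 and 5.43. For example, SD 4 with correlation 0.1 gives 4√(2 × 0.9) = 5.37. No such SD or correlation is printed.
- If the groups meant treatment sequences, 13 each would need 26 patients, and 15 are planned.

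The unpaired reading needs only the printed inputs and fits the wording, but it remains an inference. On every reading the within-patient SD is missing.

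**Step 3: what the cross-over requires.** For a paired test, λ = δ√n / σ_d on n − 1 df, where σ_d is the SD of the within-patient difference. Power is at least 80% for 4.6 if σ_d is at most 5.91 with 15 patients, or 5.43 with 13.

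With adjustment, the between-period difference in post-dose T2* is regressed on period, treatment and the between-period difference in pre-dose T2*, on n − 3 df. By simulation, the residual SD of the difference must then be at most 5.59 (15 patients) or 5.06 (13).

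**Step 4: range under stated assumptions.** The correlations below are assumptions, since the document gives none. SD is 4 at each measurement.

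Paired test, σ_d = 4√(2(1 − ρ)):

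| ρ | σ_d | Power, 15 | Power, 13 |
|---|---|---|---|
| 0 | 5.66 | 83.3% | 76.8% |
| 0.3 | 4.73 | 93.8% | 89.5% |
| 0.5 | 4.00 | 98.5% | 96.7% |

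Baseline- and period-adjusted model, same-visit correlation s and cross-visit correlation c, residual SD = 4√(2[(1 − c) − (s − c)²/(1 − c)]):

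| s, c | Residual SD | Power, 15 | Power, 13 |
|---|---|---|---|
| 0.3, 0 | 5.40 | 83% | 75% |
| 0.5, 0.1 | 4.81 | 90% | 84% |
| 0.7, 0.3 | 3.88 | 98% | 95% |

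The adjusted powers are from 200,000 simulated trials with sequences of 8 and 7, or 7 and 6. If all correlations are equal (s = c), the pre-dose difference is unrelated to the post-dose difference, and adjustment can only lose power: at 0, 0.3 and 0.5 it gives about 79, 91 and 97% with 15 patients, against 83, 93 and 98% with period alone. That case is a poor one to print.

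The figures for 13 illustrate the loss of two patients to technical failure. Withdrawn patients are replaced.

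**Step 5: the controls.** For the baseline comparison, an unpaired t-test of 15 against 15 with SD 4 has 80% power for a difference of 4.24.

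**The case against.** The strongest reply is that the mismatch does no harm. If the SD is 4, 15 patients in a paired test have 83.3% power at zero correlation, and positive correlation only raises this. That stands as an argument against any claim of a shortfall. It does not supply the justification, because it carries the SD of 4 over to these patients and assumes a correlation that the document does not state.

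A second reply is that the unpaired test is not named, and a paired calculation could also have returned 13. This is correct, and the unpaired reading is put here only as the likelier one. A paired calculation would have needed an SD of the difference that is equally unreported.

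Third, Methods says that all MRI measurements are performed twice. Averaging could reduce the relevant SD, and the document does not say whether 4 refers to single or averaged readings. Every power figure above that uses SD 4 carries that caveat.

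A reader might go further and infer that the trial is underpowered. Unadjusted change scores, with all correlations equal at 0, 0.3 and 0.5, would give 54.5, 69.7 and 83.3% with 15 patients. The Analysis section does not plan that analysis; it adjusts for baseline. Nothing in the document shows that the true within-patient SD exceeds the limits in Step 3.

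**Conclusion.** The point holds as a gap in the sample-size justification. The inputs reproduce 13 per group as an unpaired comparison of independent groups, which the drug test does not have, and the quantity that the cross-over needs is absent. The 80% is therefore not established for this design.

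The practical size depends on an unknown. With 15 patients, power is at least 80% if the SD of the difference is at most 5.9 (paired), or the residual SD at most 5.6 (adjusted). Under the assumptions tabulated, power runs from about 83% to 98.5% with 15 patients and from 75% to 97% with 13. Inadequate power is not shown, and the arithmetic on the printed inputs is sound. The point should be corrected, but it is no reason to change enrolment.

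**What to change.** Keep 15 patients and 15 controls. Replace the per-group sentence with a total for the cross-over, for example:

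> Fifteen patients enter the cross-over. For the within-patient dapagliflozin-minus-placebo difference in medullary T2*, the SD of the difference is [value, source], giving [power] for a difference of 4.6.

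If no source exists:

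> No within-patient SD was available. Fifteen patients give at least 80% power for 4.6 if the SD of the difference is at most 5.9 (13 patients: 5.4) in a paired test, or if the residual SD of the difference is at most 5.6 (13 patients: 5.1) with period and baseline adjustment.

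Follow this with the two ranges in Step 4, labelled as assumptions. For the controls, say only that 15 against 15 with SD 4 detects a baseline difference of about 4.2 with 80% power by the unpaired t-test already planned.

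In the Analysis section, state that the intervention model includes patient and period as well as the baseline value, so that power and analysis match.

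The cost is one rewritten paragraph, one sentence on the model, and a search for a within-patient SD. The added terms do change the written analysis model, so the edit is more than cosmetic. Enrolment, procedures, end-points and time points are untouched. The downside is that if the correlation is near 0 and technical failures leave 13 patients, the stated power falls below 80%.
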